#### 4. ANALYSIS SAMPLES

The summary descriptive analyses will be performed on the following subject populations:

1. All subjects who give informed consent and undergo the screening liver biopsy (Safety Sample).
2. The Intent-to-treat I sample (ITT1) will be defined as all subjects who initiate IS withdrawal
3. The Intent-to-treat II sample (ITT2) will be defined as all subjects who receive darTregs.
4. The Per-Protocol sample (PP) will be defined as all subjects who receive at least 300 x 10^6 cells of darTregs.

## 5. STUDY SUBJECTS

### 5.1. Disposition of Subjects

The disposition of all enrolled subjects will be summarized in tables and listed.

The numbers and percentages of subjects in each analysis sample, and completing each tapering level, as well as reasons for early termination from the study will be presented. For subjects discontinuing study treatment early, the reasons for discontinuing study treatment early will also be presented.

### 5.2. Demographic and Other Baseline Characteristics

Summary descriptive statistics for baseline and demographic characteristics will be reported for the ITT1, ITT2, PP samples. Characteristics to be summarized include age, race, ethnicity, sex, body weight at screening, height, time from transplant and primary reason for transplant.

## 6. STUDY OPERATIONS

### 6.1. Protocol Deviations

Protocol deviations will be listed by site with information such as type of deviation, severity of the deviation (major or non-major), date of occurrence, and the reason for the deviation. Protocol deviations will be summarized in tabular format by type of deviation.

### 6.2. Treatment Adherence

A summary of each subject's adherence to the tapering schedule will be presented in graphical form, with indications for pauses at each level and any deviations from the recommended dose at each taper level.

A summary of the number of cells infused will be presented for the darTregs as well as a categorical summary of the number of subjects that received between 100 and  $300 \times 10^6$  cells of darTregs, and the number of subjects that received at least  $300 \times 10^6$  cells of darTregs.

## 7. ENDPOINT EVALUATION

### 7.1. Overview of Analysis Methods

#### 7.1.1. Multicenter Studies

Study subjects will be recruited from three study sites. Due to the small number of subjects in the study, study data will be analyzed as a whole, and no formal accommodation for site-to-site variation will be made.

#### 7.1.2. Assessment Time Windows

Allowable visit windows for all scheduled visits are provided in Table 7-1.

**Table 7-1 Visit Windows**

High Frequency SOE Visit Windows	
Study Visit	Visit Window
Study Entry Eligibility Screening Visit (Screen 1)	Eligibility labs and biopsy should be within 8 weeks prior to initiation of IS withdrawal
Remote Visits (Telephone and Local Liver Tests)	± 3 days
Transplant Center Visits	± 14 days
Recipient PBMC Collection for Manufacturing	17 (UCSF) or 18 (Mayo) days before darTreg infusion
Medium Frequency SOE Visit Windows	
Study Visit	Visit Window
Entry into Medium Frequency SOE	Within 2 weeks after rejection (Appendix 7) Within 4 weeks after completing high frequency SOE (Appendix 8)
Week 2 (Appendix 7)	± 3 days
Remote Visits (Telephone and Local Liver Tests)	± 5 days
End of Study	± 14 days
darTregs Infusion SOE Visit Windows	
Study Visit	Visit Window
darTregs Eligibility Screening Visit	Between day 14-41 of the 2 nd withdrawal step (10-13 weeks)
Treg Blood Draw for darTregs manufacturing	Between day 18-45 of the 2 nd withdrawal step
Day 0 = darTregs Infusion	During the last 2 weeks of the 2 nd withdrawal step
Day 1 after darTregs infusion	± 1 hour
Protocol biopsy visit after darTregs infusion	Between 6-10 days after darTregs infusion
Resumption of IS withdrawal	Between day 1-14 after darTregs infusion; corresponds to between day 36 – day 63 of the 2 nd withdrawal step
Day 14 after darTregs infusion	± 2 days

Unscheduled visits may also occur throughout the study. All data will be included in analyses, regardless of time of assessment.

## **7.2. Primary Efficacy Endpoint**

The primary efficacy endpoint is the number and proportion of subjects who reduce CNI by 75% and discontinue a 2nd IS drug, if applicable, with stable liver tests for at least 12 weeks.

### **7.2.1. Computation of the Primary Efficacy Endpoint**

All subjects that successfully complete Step 5 of the tapering algorithm and have stable liver tests (ALT and alkaline phosphatase or GGT either  $\leq 1.5 \times$  upper limit of normal or  $\leq 1.5 \times$  baseline) for at least 12 weeks will be counted as meeting the primary efficacy endpoint

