Secondary Safety Endpoint	The trial will assess the safety of IS withdrawal in the context of darTregs therapy by describing the following secondary safety endpoints: 
 
1. Rate of composite outcome measure including refractory acute rejection, chronic rejection, re- transplantation, and death
 
2. Incidence of biopsy proven or clinical acute rejection and/or chronic rejection
 
3. Timing of biopsy proven or clinical acute rejection and/or chronic rejection
 
4. Severity of biopsy proven acute rejection and/or chronic rejection
 

Primary Efficacy Endpoint	The efficacy of a single IV dose of darTregs will be assessed by the number and proportion of LT subjects who are able to reduce CNI dosing by 75% and discontinue a 2 nd IS drug (if applicable) with stable liver tests for at least 12 weeks. The frequency of successful CNI minimization will be compared to historical cohorts of comparable adult LT recipients undergoing IS withdrawal.
Secondary Efficacy Endpoints	The efficacy of a single IV dose of darTregs infusion will be assessed by determining the number and percentage of subjects who have received darTregs and are identified as operationally tolerant, defined by maintaining stable allograft function (assessed by liver tests) and histology (determined by central pathologist reading in comparison to screening liver biopsy at study entry) in the absence of IS for one year. The frequency of tolerance will be compared to historical cohorts of adult liver transplant recipients undergoing IS withdrawal.
Primary Mechanistic Endpoints	The level and persistence of deuterium-labeled darTregs in the circulation will be determined by serial measurements of deuterium content in DNA from purified peripheral blood Tregs after darTregs infusion using gas chromatography-mass spectrometry (GC-MS) testing.
Secondary Mechanistic Endpoints	The overall increase of darTregs in circulation will be assessed using the alloreactive T cell frequency (ATF) assay

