darTregs Infusion Inclusion Criteria	
Subjects will initiate IS withdrawal and, at the beginning of the 2nd step of the withdrawal algorithm (week 1-2), undergo a final assessment to ensure eligibility for darTregs infusion. Subjects must meet the following criteria to receive darTregs infusion:
 
 
1. Stable liver tests, defined as ALT and either alkaline phosphatase or GGT either within normal limits OR <1.5 X baseline
 
2. No detectable circulating EBV or CMV DNA prior to darTregs infusion, assessed at the time of PBMC collection for manufacture
 
3. For subjects with HBV, no detectable circulating HBV DNA prior to darTreg infusion, assessed at the time of PBMC collection for manufacture
 
4. Able to understand and provide informed consent
 

darTregs Infusion Exclusion Criteria	
Subjects who meet any of these criteria are not eligible for darTregs infusion:
 
 
1. Diagnosis of AR after initiation of IS withdrawal
 
2. Any vaccination given within 28 days prior to Treg collection for Treg production
 
3. Receipt of a vaccination within 14 days prior to Treg infusion
 
4. Unacceptable darTregs product
 
5. Positive pregnancy test
 
6. Clinical evidence of viral syndrome less than 7 days prior to darTregs infusion
 

Field Code Changed

Eligibility Criteria to Resume IS Withdrawal after darTregs infusion	Subjects are eligible to resume IS withdrawal after darTregs infusion if all criteria below are met: 1. Subject received at least $100 \times 10^6$ darTregs 2. ALT and either alkaline phosphatase or GGT remain within normal limits or $\leq 1.5 \times$ baseline after darTregs infusion 3. For subjects with elevated liver tests as defined above, local pathology reading of liver biopsy 6-10 days after darTregs infusion is without acute rejection according to Banff criteria 4. IS withdrawal resumes no later than 14 days after darTregs infusion 5. Site principal investigator determines it is acceptable for the study subject to resume IS withdrawal

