### **7.2.2. Primary Analysis of the Primary Efficacy Endpoint**

The primary efficacy endpoint will be descriptively summarized with an exact binomial proportion and an exact 95% confidence interval using the ITT1 population.

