### **7.2.3. Sensitivity Analyses of the Primary Efficacy Endpoint**

A sensitivity analysis using both the ITT2 and PP populations will also be performed.

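### Does the looser liver-test limit in SAP Section 7.2.1, compared with the eligibility criteria, leave the primary efficacy endpoint badly defined?

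*SAP*

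**What the plan says.** The Synopsis and the opening of SAP Section 7.2 state the primary efficacy endpoint with the bare term *stable liver tests* and no cut-off. Section 7.2.1 supplies one. A success must "complete Step 5 of the tapering algorithm and have stable liver tests (ALT and alkaline phosphatase or GGT either" at most 1.5 × "upper limit of normal or" at most 1.5 × baseline, for 12 weeks or more.

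Liver-test limits also appear in three sets of Synopsis criteria:

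- **Enrollment:** absolute limits (ALT below 60 U/L, with alkaline phosphatase below 150 U/L or GGT below 60 U/L).
- **darTregs infusion, inclusion criterion 1:** "Stable liver tests, defined as ALT and either alkaline phosphatase or GGT either within normal limits OR" below 1.5 × baseline.
- **Resuming withdrawal after infusion, criterion 2:** "ALT and either alkaline phosphatase or GGT remain within normal limits or" at most 1.5 × baseline. Criterion 3 then begins "For subjects with elevated liver tests as defined above" and asks for a biopsy reading without acute rejection.

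The primary analysis (Section 7.2.2) is a proportion with an "exact 95% confidence interval using the ITT1 population". Section 7.2.3 adds: "A sensitivity analysis using both the ITT2 and PP populations will also be performed". It plans no re-scoring under another liver-test limit.

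**The concern.** One term carries two numeric meanings, and the looser one scores the primary efficacy endpoint. The infusion criterion is the only place that uses the words *defined as* for the term, so a reader could take it as the trial's definition and see Section 7.2.1 as an unannounced relaxation. The same value can then get opposite labels: elevated when deciding whether withdrawal may resume, stable when counting successes.

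Among subjects who complete Step 5, the looser limit can only turn failures into successes. The trial is open-label without a control arm, and the Synopsis says: "The frequency of successful CNI minimization will be compared to historical cohorts". A lenient success rule could flatter that comparison. Because the sensitivity analyses change only the analysis population, no planned table would show how much of the success count depends on the limit.

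**Working it through.** The SAP gives no figure on this point to reproduce, so the check compares the rules directly.

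**1. The two ceilings.** Let *b* be a subject's baseline and *U* the ULN.

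- Infusion criterion: max(*U*, 1.5*b*), with strict inequality on the baseline part.
- Section 7.2.1: max(1.5*U*, 1.5*b*).

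The ratio of the second to the first is:

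- 1.5 when *b* ≤ *U*/1.5;
- *U*/*b* when *b* lies between *U*/1.5 and *U*;
- 1 when *b* ≥ *U*.

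So the endpoint limit is never tighter, and it is looser only for baselines below ULN.

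**2. Illustration.** The SAP gives no ULN. The ALT values of 35, 40 and 55 U/L are assumptions.

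| Assumed ULN | Baseline | Infusion ceiling | Section 7.2.1 ceiling | Ratio |
|---|---|---|---|---|
| 35 | 20 | 35 | 52.5 | 1.50 |
| 40 | 20 | 40 | 60 | 1.50 |
| 40 | 30 | 45 | 60 | 1.33 |
| 40 | 40 | 60 | 60 | 1.00 |
| 55 | 20 | 55 | 82.5 | 1.50 |

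With ULN 40 and baseline 20, an ALT of 55 exceeds both 40 and 1.5 × 20 = 30, so the resumption criteria call it elevated. It is below 60, so Section 7.2.1 calls it stable.

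**3. Effect of one subject.** ITT1 is everyone who starts withdrawal. The accrual objective is up to 18 enrolled, to reach up to 11 eligible for both interventions, so *n* is assumed to be 11 to 18. One subject is 1/18 = 5.6 or 1/11 = 9.1 percentage points. Examples with Clopper-Pearson 95% intervals:

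- *n* = 11: 4/11 = 36.4% (10.9 to 69.2) against 5/11 = 45.5% (16.7 to 76.6).
- *n* = 18: 6/18 = 33.3% (13.3 to 59.0) against 7/18 = 38.9% (17.3 to 64.3).

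The one-subject shift is small beside intervals 46 to 60 points wide. It is also simply 1/*n*, the same for any cause of reclassification.

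**4. Which rule governs the count.** Section 7.2.1 is headed as the computation of the primary efficacy endpoint and puts its limits in parentheses straight after the term. The other limits sit in eligibility lists and serve decisions around the infusion. An analyst following the SAP has one rule for the endpoint.

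**5. The missing word.** Section 7.2.1 omits *either* before alkaline phosphatase, so in strict grammar GGT alone might seem to suffice. The enrollment, infusion and resumption criteria all require ALT together with one of the other two tests. That is the natural reading here as well.

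**The case for a change.** The strongest case for a change is that the difference is real, runs in one direction, affects the primary endpoint, and is nowhere called intentional. Stating the intention and adding one table row would cost little, since the liver tests are collected anyway. In an open-label, uncontrolled trial such matters are best settled before analysis.

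The facts in that case stand. The inference to a defect does not:

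- The SAP sets liver-test limits by purpose, with absolute values at enrollment and relative ones at infusion and at resumption. A separate limit for the outcome fits that pattern. The protocol, not at hand, may give its reason.
- Calling the endpoint limit lenient takes the infusion criterion as the reference, which the SAP never does.
- The SAP does not say what limit the historical cohorts used. Scoring by the infusion criterion could bring the comparison closer or take it further away.
- The liver-test values are not hidden. Section 8.4 plans plots with one line per subject over time and normal ranges marked. This is not a formal re-scoring, but with at most 18 enrolled subjects a reader can see who ran above normal.
- Re-scoring by a pre-infusion criterion is one of many possible sensitivity analyses, and leaving it out is not an error.

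**Conclusion.** The concern does not call for a change. The texts differ as described, and the endpoint ceiling is up to 50% higher for baselines below ULN, a result that holds for any ULN. But Section 7.2.1 fixes the endpoint explicitly, the tighter limits serve other decisions, and the analysis is descriptive with no test or error rate to distort.

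The possible effect is 5.6 to 9.1 points per reclassified subject, if ITT1 holds 11 to 18. It arises only for someone who completes Step 5, has a baseline below ULN for a test that counts, and has values in the band between the two limits. Whether any such subject exists cannot be known from the SAP.

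The unexplained difference and the dropped *either* are matters of wording that an analyst resolves from the SAP itself. Which limit is clinically preferable is not judged here.

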### **7.2.2. Primary Analysis of the Primary Efficacy Endpoint**

The primary efficacy endpoint will be descriptively summarized with an exact binomial proportion and an exact 95% confidence interval using the ITT1 population.

### **7.2.3. Sensitivity Analyses of the Primary Efficacy Endpoint**

A sensitivity analysis using both the ITT2 and PP populations will also be performed.

## **7.3. Primary Safety Endpoint**

The primary safety endpoint is a descriptive analysis of three outcomes assessed 24 weeks after darTregs:

- CTCAE Grade 3 or higher AEs attributable to the darTregs infusion including infusion reaction / cytokine release syndrome
- study defined Grade 3 or higher infections (Protocol section 14.3.1)
- any malignancy, including PTLD

### **7.3.1. Computation of the Primary Safety Endpoint**

All subjects who have any of the listed outcomes above will be counted as meeting the primary safety endpoint.

### **7.3.2. Primary Analysis of the Primary Safety Endpoint**

The primary safety endpoint will be descriptively summarized with an exact binomial proportion and an exact 95% confidence interval using the ITT1 population.

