### **7.3.3. Additional Analyses of the Primary Safety Endpoint**

The outcomes in the primary safety endpoint will also be analyzed individually. A sensitivity analysis using the PP population will also be performed.

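### The primary safety endpoint is timed from the darTregs infusion but analysed in everyone who starts IS withdrawal (ITT1), and no analysis specified for it uses all infused subjects (ITT2)

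*SAP*

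**What the plan says.** SAP 7.3 sets the time origin of the endpoint: "The primary safety endpoint is a descriptive analysis of three outcomes assessed 24 weeks after darTregs". The three outcomes are Grade 3 or higher AEs attributable to the infusion, study-defined Grade 3 or higher infections, and any malignancy. SAP 7.3.1 gives the counting rule: "All subjects who have any of the listed outcomes above will be counted as meeting the primary safety endpoint". SAP 7.3.2 then fixes the population: "The primary safety endpoint will be descriptively summarized with an exact binomial proportion and an exact 95% confidence interval using the ITT1 population".

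In SAP section 4, ITT1 "will be defined as all subjects who initiate IS withdrawal" and ITT2 "will be defined as all subjects who receive darTregs". PP is the subset given at least 300 x 10^6 cells.

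The Study Design row of the synopsis (SAP section 1) places infusion 12 to 14 weeks after withdrawal starts. The infusion exclusion criteria in the synopsis bar some subjects who have already started withdrawal, including those with "Diagnosis of AR after initiation of IS withdrawal" or "Unacceptable darTregs product".

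For further analyses of this endpoint, SAP 7.3.3 analyses the three outcomes individually, naming no population of its own, and adds: "A sensitivity analysis using the PP population will also be performed". ITT2 is not mentioned in 7.3.

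**The concern.** The primary safety objective is the safety and tolerability of one dose of darTregs. The natural denominator is the people who received it. ITT1 is defined at an earlier point and can contain people who never did.

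A never-infused subject has no 24-week post-infusion assessment and cannot contribute an infusion-attributable event. The SAP does not say how to count such a subject. The subject might be entered as event-free, which dilutes the proportion and lowers the upper confidence limit. Alternatively, the rule in 7.3.1 might be applied without regard to infusion, and an infection or malignancy with no connection to darTregs would then be counted. In neither case does the ITT1 proportion estimate the event rate among infused subjects.

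The study is single-arm, so there is no randomised comparison for an intention-to-treat set to protect. For infusion-attributable events, adding unexposed subjects can only make the product look safer.

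**Working it through.** The SAP gives no sample-size justification, expected rate or margin for this endpoint, so there is no stated figure to reproduce. The check has two parts.

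**1. Which population covers all infused subjects and only them?**

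| Population | Includes never-infused subjects? | Includes all infused subjects? | Named for the primary safety endpoint? |
|---|---|---|---|
| ITT1 | Can | Yes, as infusion follows the start of withdrawal | Yes, primary (7.3.2) |
| ITT2 | No | Yes | No |
| PP | No | No, omits those below 300 x 10^6 cells | Yes, sensitivity (7.3.3) |
| Safety sample | Can | Yes, as the screening biopsy precedes withdrawal | No; used for the general AE tables (8.1) |

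The group PP omits is foreseen: SAP 6.2 plans a count of subjects given 100 to 300 x 10^6 cells. ITT2 is used elsewhere, for the primary efficacy sensitivity analysis (7.2.3), the secondary efficacy endpoints (7.4), and rejection timing and severity (7.5.3, 7.5.4).

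**2. How much can the denominator matter?**

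Inputs:
- Infused subjects: 11, an assumption taken from the accrual target of up to 11 (synopsis, Accrual Objective).
- ITT1 size: not stated, so varied from 11 to 18. The 18 is a ceiling, because it counts subjects screened and enrolled, and screening can exclude some before withdrawal starts.
- Interval: exact (Clopper-Pearson) 95%, as 7.3.2 specifies.

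Formulas for x events in n subjects: lower limit = the 0.025 quantile of Beta(x, n − x + 1), or 0 if x = 0; upper limit = the 0.975 quantile of Beta(x + 1, n − x). For x = 0 the upper limit reduces to 1 − 0.025^(1/n). For n = 11 this is 1 − 0.025^(1/11) = 28.5%; for n = 14 it is 1 − 0.025^(1/14) = 23.2%.

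Results when any event is in an infused subject:

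| Denominator | 0 events: upper limit | 1 event: proportion (95% CI) |
|---|---|---|
| 11 (ITT2, or ITT1 if all are infused) | 28.5% | 9.1% (0.2–41.3) |
| ITT1 = 12 | 26.5% | 8.3% (0.2–38.5) |
| ITT1 = 13 | 24.7% | 7.7% (0.2–36.0) |
| ITT1 = 14 | 23.2% | 7.1% (0.2–33.9) |
| ITT1 = 15 | 21.8% | 6.7% (0.2–31.9) |
| ITT1 = 18 | 18.5% | 5.6% (0.1–27.3) |

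If events occur only in infused subjects, the ITT1 proportion is the infused proportion times 11/N, where N is the size of ITT1. A true rate of 30% among the infused would appear on average as 30% × 11/13 = 25.4%, 30% × 11/15 = 22.0%, or 30% × 11/18 = 18.3%. At that 30% rate the nominal 95% interval still covers the infused rate with probability 97.6% and 98.0% at N = 13 and 15. At N = 18 coverage falls to 88.7%, against 95.9% with ITT2.

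Opposite direction, if 7.3.1 is applied regardless of infusion: no events among 11 infused and one Grade 3 infection in a never-infused subject, with ITT1 = 14, is reported as 1/14 = 7.1% (0.2–33.9). Among the infused it is 0/11 (0–28.5).

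PP gap: if 2 of the 11 receive fewer than 300 x 10^6 cells and one of those two has the only event, PP shows 0/9 (upper limit 33.6%). ITT2 would show 1/11 = 9.1%.

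**The case against.** The strongest reply is that little depends on this interval. The analysis is descriptive, and the SAP attaches no test, margin or decision to it. The pauses for DSMB review are triggered by events, whatever the denominator. SAP 5.1 reports the size of each sample and 7.3.3 reports the outcomes separately, so for infusion-attributable AEs a reader can work out the rate among the infused. This stands, and it limits the consequence to reporting. The recovery is not assured for infections and malignancies, because 7.3 does not split them by infusion status.

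A second point is that the upward direction depends on reading 7.3.1 apart from 7.3. Read together, a never-infused subject has no outcome at 24 weeks after darTregs and might not be counted. That is fair: dilution is the better-supported direction, and inflation is only possible because the text is silent.

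Third, the lead-in to section 4 says descriptive summaries will be done on all four samples, ITT2 among them. This is a general statement. Sections 7.3.2 and 7.3.3 name specific populations and omit ITT2, whereas 7.2.3 names it.

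Finally, IS reduction is itself one of the two primary interventions, so an ITT1 summary has meaning for the strategy as a whole, and adding ITT2 as a sensitivity analysis might be enough. But the secondary safety endpoints already address withdrawal safety, in ITT1 by default (7.5). The primary safety objective concerns the darTregs dose, so a supporting table would leave the headline result in the wrong population.

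**Conclusion.** The concern holds. As written, the primary safety proportion and interval need not describe the subjects who received darTregs, and the 24-week window is undefined for any ITT1 subject who is not infused.

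The size depends on how many such subjects there are, which the SAP does not indicate. With 11 infused and no events, one never-infused subject moves the upper limit by 2.0 percentage points (28.5% to 26.5%) and three move it by 5.3 points (28.5% to 23.2%). The extreme case of ITT1 = 18 moves it by 10.0 points (to 18.5%). With every ITT1 subject infused, the difference is zero. The effect is confined to reporting, but it falls on the trial's primary safety result and should be corrected before analysis.

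**What to change.** - In 7.3.2, replace ITT1 with ITT2 and state that events are counted from infusion to week 24.
- In 7.3.3, analyse the three outcomes individually in ITT2 and keep PP as the sensitivity analysis.
- Report events before infusion, and events in ITT1 subjects who are never infused, in a separate table as safety of IS withdrawal.
- If the protocol, which was not available here, names ITT1 for this endpoint, record the change in SAP section 10, which has a heading but no content.

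The cost is an edit to two subsections, one added table and possibly a section 10 entry. No new data are needed. The reported interval may be wider and less favourable than the one now planned. Making the change before analysis avoids choosing a denominator after the events are known.
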